#### Medical

18. The patient has any other medical disease for which the treatment takes priority over treatment of schizophrenia or is likely to interfere with study treatment or impair treatment compliance.
19. The patient has a history of moderate or severe head trauma or other neurological disorders or systemic medical diseases that are, in the investigator's opinion, likely to affect central nervous system functioning.
20. The patient has epilepsy or a history of seizures, except for a single seizure episode (e.g., childhood febrile seizure, post traumatic, or alcohol withdrawal).
21. The patient has or has had one or more of the following conditions that is/are considered clinically relevant in the context of the study:
  - neurological disorder
  - cardiovascular disease
  - seizure disorder or encephalopathy
  - congestive heart failure
  - cardiac hypertrophy
  - arrhythmia
  - bradycardia (pulse <50 bpm)
  - respiratory disease
  - hepatic impairment or renal insufficiency
  - metabolic disorder
  - endocrine disorder
  - gastrointestinal disorder
  - haematological disorder
  - infectious disorder
  - any clinically significant immunological condition
  - dermatological disorder

- venereal disease
  - elevated intra-ocular pressure or is at risk of acute narrow-angle glaucoma
22. The patient has clinically significant abnormal vital signs.
23. The patient has one or more clinical laboratory test values outside the reference range, based on the blood and urine samples taken at the Screening Visit, that are of potential risk to the patient's safety, or the patient has, at the Screening Visit:
- a serum creatinine value >1.5 times the upper limit of the reference range
  - a serum total bilirubin value >1.5 times the upper limit of the reference range
  - a serum alanine aminotransferase (ALT) or aspartate aminotransferase (AST) value >2 times the upper limit of the reference range
24. The patient has not previously been diagnosed with diabetes, but meets ANY of the following criteria (newly diagnosed diabetes):
- HbA1C >6.5%, OR
  - Fasting plasma glucose >126 mg/dL (7.0 mmol/L), OR
  - Non-fasting plasma glucose >200 mg/dL (11.1 mmol).
25. The patient has previously been diagnosed with diabetes, but the condition is unstable as determined by ANY of the following criteria:
- HbA1c  $\geq$ 7.0%, OR
  - Screening glucose is >6.94 mmol/L (fasting, >125 mg/dL) or 11.1 mmol/L (nonfasting, 200 mg/dL). If the non-fasting screening glucose is 11.1 mmol/L (200 mg/dL), patients must be retested in a fasted state and the retest value must be  $\leq$ 6.94 mmol/L (125 mg/dL) to be eligible for the study, OR
  - The patient has not been maintained on a stable regimen of insulin and/or oral antidiabetic medication(s) for at least 28 days prior to Screening or the diabetes has not been well-controlled by diet for at least 28 days prior to Screening, OR
  - The patient has been hospitalized within 6 months prior to Screening due to diabetes or complications related to diabetes
26. The patient has orthostatic hypotension (defined as a decrease in systolic blood pressure >20 mmHg between two measurements, first in the supine position and then sitting, and standing after the patient has rested in each position for at least 3 minutes.
27. The patient has, at the Screening or at the Baseline Visit:
- an abnormal ECG that is, in the investigator's opinion, clinically significant
  - a PR interval >250 ms
  - a QRS interval >130 ms
  - a QTcF interval >450 ms (for men) or >470 ms (for women) (based on the Fridericia correction where  $QTcF = QT/RR^{0.33}$ )
  - A patient should also be excluded if he or she has any other abnormal ECG tests that in the investigator's judgment are medically significant and would impact the safety of the patient or the interpretation of the study results.
28. The patient has a history of cancer, other than basal cell or Stage 1 squamous cell carcinoma of the skin, that has not been in remission for >5 years prior to the first dose of IMP.

## 5.4 Withdrawal Criteria

A patient must be withdrawn from the study if:

- the patient and/or his or her legal representative (if applicable) withdraw(s) his or her consent (defined as a patient and/or his or her legal representative [if applicable] who explicitly take(s) back his or her consent); section 8.4 states how the patient's data will be handled
- the patient is lost to follow-up (defined as a patient who fails to comply with scheduled study visits or contact, who has not actively withdrawn from the study, and for whom no alternative contact information is available [this implies that at least two documented attempts have been made to contact the patient via both phone and mail]).

A patient must be withdrawn from treatment if:

- the investigator considers it, for safety, lack of efficacy, and/or study compliance reasons, in the best interests of the patient that he or she be withdrawn
- the patient becomes pregnant
- the patient has a serum ALT or AST value >3 times the upper limit of the reference range and a serum total bilirubin value >2 times the upper limit of the reference range
- the patient has a serum ALT or AST value >5 times the upper limit of the reference range that is confirmed by testing <2 weeks later
- the patient has a QTcF interval >500 ms or a change from Screening (or from Baseline for *16159A-patients* and *16323A-patients*) in the QTcF interval >60 ms concurrently with a QTcF interval >470 ms
- the patient has a positive urine drug screen verified by repeated testing at the following site visit
- the patient fails to comply with study procedures
- the patient is <80% IMP compliant between two consecutive, scheduled visits
- the patient in the opinion of the investigator has significant risk of suicide or who answers "Yes" to suicidal ideation questions 4 or 5 or answers "Yes" to suicidal behaviour on the C-SSRS® at any time during the study

Patients who withdraw will not be replaced.

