**Investigational Medicinal Products, Doses and Mode of Administration**

Lu AF35700 – 10, 20 mg/day; tablets, orally, once daily

Lu AF35700 – 70 mg/week; tablets, orally, once weekly

Tablets will be taken in the morning or evening.

For 16159A-patients

- In addition, during the first week of study 16159B, *16159A-patients* will receive (in a blinded fashion) a down-titration wallet from study 16159A.
- For patients who were randomised to risperidone or olanzapine in study 16159A, the discontinuation of risperidone or olanzapine will be done according to the following scheme:
  - Risperidone: 4 mg/day for the first 3 days; 2 mg/day for the 4 subsequent days, encapsulated tablets, orally, once daily
  - Olanzapine: 10 mg/day for the first 3 days; 5 mg/day for the 4 subsequent days, encapsulated tablets, orally, once daily
- For patients who were randomised to Lu AF35700 in study 16159A, the Lu AF35700 encapsulated tablets will be stopped and patients will receive placebo for 7 days, encapsulated tablets, orally, once daily.

For 16323A-patients

- In addition, during the first week of study 16159B, *16323A-patients* will receive (in a blinded fashion) a down-titration wallet from study 16323A.
- For patients who were randomised to quetiapine, the discontinuation of quetiapine will be done according to the following scheme:
  - Quetiapine: 600 mg/day for the first 3 days; 300 mg/day for the 4 subsequent days, encapsulated tablets, orally, once daily.
- For patients who were randomised to Lu AF35700, the Lu AF35700 encapsulated tablets will be stopped and patients will receive placebo for 7 days, encapsulated tablets, orally, once daily.

For Other Patients

- The treatment with Lu AF35700 tablets will be initiated at daily dose of 10 mg at Day 1 of study 16159B, while the discontinuation of the current oral antipsychotic medication will be gradually down-titrated according to the corresponding current SmPC or equivalent document/label and will be completed at Day 7.

For all patients

- Dose adjustments for efficacy or tolerability are allowed according to the investigator's clinical judgement based on the patient's response and tolerability to treatment.

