**For patients who completed study 16159A (*16159A-patients*)**

The Baseline Visit will take place at the same visit as the Visit 12 (Primary Outcome Visit, end of Week 16) of the study 16159A.

After the baseline assessment, for eligible patients, the treatment with Lu AF35700 will be initiated at daily dose of 10 mg at Day 1 of study 16159B. In addition, for *16159A-patients*, the treatment (Lu AF35700, risperidone or olanzapine) received during study 16159A will be tapered down in a blinded fashion with wallets from study 16159A and will be completed in 7 days according to the following scheme:

- Patients randomised to Risperidone: 4 mg/day for the first 3 days; 2 mg/day for the 4 subsequent days, encapsulated tablets, orally, once daily
- Patients randomised to Olanzapine: 10 mg/day for the first 3 days; 5 mg/day for the 4 subsequent days, encapsulated tablets, orally, once daily
- Patients randomised to Lu AF35700: Placebo for 7 days, encapsulated tablets, orally, once daily.

At the end of the first week (Week 1 Visit), all patients will be treated with 10 mg/day Lu AF35700 only.

From the Week 1 Visit, according to the investigator's clinical judgment, the 10 mg/day dose can be increased to 20 mg/day based on the patient's response. Thereafter, the 20 mg/day dose can be reduced to 10 mg/day based on the patient's tolerability to treatment. This can occur at scheduled or unscheduled visits.

From the Week 8 Visit, the switch from Lu AF35700 daily dosing regimen to Lu AF35700 weekly dosing regimen can be performed at any consecutive visit according to the investigator's clinical judgment. The first weekly tablet will be taken 7 days after the last daily tablet. The Lu AF35700 weekly dosing regimen can be switched back to a daily dosing regimen of 10 mg/day for tolerability reasons or to 20 mg/day for worsening of the patient's clinical status. This can occur at scheduled or unscheduled visits. The first daily tablet will be taken 7 days after the last weekly tablet.

The number of patients under weekly dosing regimen will be limited to 50 patients by IVRS/IWRS.

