## **9.7 Treatment Compliance**

The responsible study personnel will dispense the IMPs. Accountability and compliance verification should be documented in the patient's source documents. Patients must be counselled on the importance of taking the study medications as directed at all study visits.

The medical monitor should be contacted if the investigator is uncertain whether a patient's lack of compliance warrants withdrawal from the study.

Patients must be counselled on the importance of taking the IMP as directed at all study visits.

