Recent and concomitant medication will be coded using the *WHO Drug Dictionary* (WHO-DDE).

Medications will be classified according to the start and stop time and summarized by anatomical therapeutic chemical (ATC) code levels 2 and 3, generic drug name, previous treatment group, and for each of the categories:

- Medication started before first dose of IMP (i.e. on-going concomitant medication from the lead-in study) and continued after first dose of IMP
- Concomitant medication started at or after first dose of IMP

The tables will be based on the APTS.

10 Exposure and Compliance

Exposure (days) to IMP in study 16159B will be calculated as:

$$\text{Last date of IMP} - \text{Start date of IMP} + 1$$

For details about handling of missing IMP start or stop date, see section 19.3.1 (IMP Start and Stop Dates).

The exposure for patients on the weekly dosing regimen will be summarized together with the exposure for patients on the daily dosing regimens.

Exposure to IMP will be summarized overall and by previous treatment group using descriptive statistics, and summaries will include the patient years of exposure (PYE). PYE will be calculated as the sum of the number of days of exposure to IMP for each patient, divided by 365.25 days.

In addition, exposure to IMP will be categorized in intervals 1 – 84 days [0 – 3 months], 85 – 168 days [3 – 6 months], 169 – 252 days [6 – 9 months], 253 – 336 days [9 – 12 months], > 336 days [>12 months], and summarized overall and by previous treatment group.

The final dose level for patients in APTS will be summarized overall and by previous treatment group.

The number of patients switching to the weekly dosing regimen will be summarized based on the APTS. The summary will include the number of patients going back to daily dosing after initiating weekly dosing.

Non-compliant days are days on which no IMP has been taken, less than the full dose of IMP has been taken, or more than the full dose of IMP has been taken.

Compliance (%) with IMP for the Treatment Period will be calculated as:

$$\frac{\text{Last date of IMP} - \text{Start date of IMP} + 1 - \text{Number of non-compliant days}}{\text{Last date of IMP} - \text{Start date of IMP} + 1} \times 100$$

where the number of non-compliant days is defined as the sum of all non-compliant days from the start of the interval to the end of the interval.

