The compliance for patients on the weekly dosing regimen will be summarized together with the compliance for patients on the daily dosing regimens.

Compliance with IMP will be categorized as “≤80% compliant” or “>80% compliant”. The number and percentage of patients in each category will be summarised by previous treatment group and in total based on the APTS.

Exposure and compliance will be summarized based on the APTS.

11 Efficacy

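### SAP section 10 scores adherent weekly-dosing patients as non-compliant, and the <80% withdrawal rule in protocol 5.4 takes no account of regimen

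*Protocol*

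**What the plan says.** **Withdrawal rule.** Protocol 5.4 opens its list with "A patient must be withdrawn from treatment if" and includes the criterion "the patient is <80% IMP compliant between two consecutive, scheduled visits". It gives no formula for compliance and does not separate daily from weekly dosing. The same list has a judgement-based criterion, which applies when "the investigator considers it, for safety, lack of efficacy, and/or study compliance reasons, in the best interests of the patient" to stop. Protocol 14 states a no-waiver policy.

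**Medical monitor.** Protocol 9.7 sends an investigator who is unsure to the medical monitor, on the question whether "lack of compliance warrants withdrawal from the study". It does not cite the 80% threshold, and it speaks of the study where 5.4 speaks of treatment.

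**Weekly regimen.** It is "70 mg/week; tablets, orally, once weekly", for 16159A patients only and capped at 50. Protocol 6.1 says: "From the Week 8 Visit, the switch from Lu AF35700 daily dosing regimen to Lu AF35700 weekly dosing regimen can be performed". The change may be made then or later, and switching back is allowed.

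**SAP compliance.** SAP 10 says: "Non-compliant days are days on which no IMP has been taken", or on which less or more than the full dose was taken. It subtracts these days from the days between first and last IMP date and divides by that same number of days. It adds: "The compliance for patients on the weekly dosing regimen will be summarized together with the compliance for patients on the daily dosing regimens". Patients are then classed as ≤80% or >80% compliant.

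**Description of weekly dosing.** Protocol 17.7 plans a summary of the frequency and duration of weekly dosing and of the reasons for starting and ending it. SAP 10 keeps only the number of patients who switch and the number who switch back. SAP 18 does not list this reduction among the changes.

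**The concern.** A day-based compliance measure suits a tablet taken every day. Applied to a tablet taken every seventh day, it makes six days in seven non-compliant by construction, and pooling then hides the problem inside one overall percentage.

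The withdrawal rule has a related weakness. Four weekly tablets per visit interval allow only coarse steps in percentage compliance, so a single missed tablet can cross the threshold.

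Protocol 3.2 justifies weekly dosing by its feasibility for maintenance and a possible gain in adherence. The data most relevant to that purpose are compliance on weekly dosing, how long patients stay on it and why they stop. The compliance figure would be wrong as defined. Duration and reasons for stopping could be shaped by the rule, and the planned tables would not show it, because exposure is pooled and withdrawals are tabulated only overall and by previous treatment.

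**Working it through.** The plan states no compliance or retention figure to reproduce, so this is direct arithmetic.

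**Inputs**
- Threshold: <80% per interval between scheduled visits (protocol 5.4).
- Weekly regimen: one 70 mg tablet a week, from Week 8 (protocol 6.1, 6.2).
- Scheduled visits from Week 8 to Week 52: 11 intervals of 28 days, so nominally 4 weekly or 28 daily tablets each (Panel 2).
- Visit windows: ±6 days at Week 8 and ±7 days from Week 12, so an interval can run from about 14 to 42 days, or 2 to 6 weekly tablets, if the supply dispensed allows it.
- First weekly tablet 7 days after the last daily one (protocol 3.1).
- At most 50 weekly patients; more than 500 patients included (SAP 16).

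**Step 1: SAP 10 as written, fully adherent patient**

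Compliance = (days − non-compliant days) / days × 100.
- While on weekly dosing: 1/7 = 14.3% (4/28 in a 28-day interval).
- Switch at Week 8, completing at Day 364: 56 daily tablets + 44 weekly tablets = 100 days with IMP; 100/364 = 27.5%.
- Completer with w weeks of weekly dosing: (364 − 6w)/364. For w = 12 this is 292/364 = 80.2%; for w = 13 it is 286/364 = 78.6%. From 13 weeks on, a fully adherent completer falls in the ≤80% class.

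If a programmer departs from the wording, one missed weekly tablet in 28 days gives 27/28 = 96.4% when it counts as one non-compliant day and 21/28 = 75.0% when it counts as seven. These lie on opposite sides of the cut, and the SAP does not choose.

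**Step 2: the protocol 5.4 rule on a tablet count**

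Compliance = (due − missed)/due.

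| Tablets due in interval | Missed | Compliance | <80% met? |
|---|---|---|---|
| 3 weekly (possible just after a switch) | 1 | 66.7% | yes |
| 4 weekly (nominal) | 1 | 75.0% | yes |
| 5 weekly | 1 | 80.0% | no |
| 6 weekly | 1 | 83.3% | no |
| 28 daily (nominal) | 5 | 82.1% | no |
| 28 daily (nominal) | 6 | 78.6% | yes |

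**Step 3: illustration only**

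The documents give no miss rate. Assume independent misses with the same per-dose probability p on both regimens, nominal intervals, and weekly dosing from Week 8 to Week 52. Per interval, the chance q of meeting the rule is 1 − (1 − p)^4 for weekly and P(Binomial(28, p) ≥ 6) for daily. Over 11 intervals it is 1 − (1 − q)^11.

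| p | Weekly, per interval | Daily, per interval | Weekly, 11 intervals | Daily, 11 intervals |
|---|---|---|---|---|
| 1% | 3.9% | <0.01% | 36% | <0.01% |
| 2% | 7.8% | 0.002% | 59% | 0.02% |
| 5% | 18.5% | 0.23% | 90% | 2.5% |
| 10% | 34.4% | 5.5% | 99% | 46% |

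Equal miss rates may be unfair to weekly dosing. The weekly miss rate that gives the same risk per interval is 1 − (1 − q_daily)^(1/4): 1.4% when daily patients miss 10%, and 0.06% when they miss 5%.

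**The case against.** **No retention comparison is planned.** A reader might infer that the rule spoils a comparison of retention between weekly and daily dosing. The documents do not support that. Time to withdrawal is plotted for the total group only (SAP 7.2), and the daily-only displays were dropped (SAP 18). Switching is also non-randomised, capped and reversible, so such a comparison would be confounded under any compliance rule. This stands in full.

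**Both regimens face the same percentage.** A daily patient missing 7 of 28 is also at 75% and also meets the rule. It would be wrong to say that, within an interval, weekly patients are removed at a percentage at which daily patients stay. The difference is one of granularity. This stands too, but the granularity is still 1 missed dose against 6.

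**Protocol 9.7 need not contradict 5.4.** A reader might take 9.7 as making the <80% rule discretionary. It does not say so, and it can be read as serving the judgement-based criterion in 5.4. What remains is a missing link between the two sections and the unexplained difference between leaving treatment and leaving the study, which SAP 3.3 treats as distinct.

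**The probabilities are assumed.** The 90% needs independent misses, equal per-dose miss rates and 44 weeks of weekly dosing, whereas patients may switch later or switch back. The protocol also hopes for better adherence on weekly dosing and requires a reliable caregiver. The figures show direction, not expected losses.

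**The literal SAP reading would not be used, and some data exist anyway.** SAP 10 is descriptive and withdraws nobody. SAP 7.2 lists each withdrawal with its reasons, and SAP 12.1 tabulates adverse events on weekly dosing. But a definition that has to be overridden needs a written replacement, since the plausible alternatives give 96.4% or 75.0%. Listings also do not replace the summary promised in protocol 17.7.

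**Conclusion.** The SAP part is firm. As written, the compliance rule gives a wrong result for weekly dosing: about 27% for a fully adherent patient who switches at Week 8 and completes, and ≤80% for any fully adherent completer with 13 or more weeks of it. With at most 50 such patients among more than 500, the pooled ≤80% share could be inflated by up to about 10 percentage points (50/500), and compliance on weekly dosing could not be read at all.

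The protocol part is conditional. On a tablet count over a nominal 28-day interval, one missed weekly tablet meets the mandatory rule, against six daily tablets. It does not when 5 or 6 weekly tablets fall in the interval, and the protocol never says how compliance is computed. The rule may therefore shorten weekly exposure and affect the descriptive duration, termination and adherence data. How often depends on miss rates that the documents do not give.

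**What to change.** **SAP 10.** Define compliance as scheduled doses taken over scheduled doses due. With one dose due per day this matches the present formula for daily patients, provided that partial and excess doses still count as non-compliant. The tablet-free days of weekly dosing, and those around a switch, then drop out. Align the boundary convention: exactly 80% is not a withdrawal under protocol 5.4 (<80%) but falls in the SAP's ≤80% class.

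**SAP 7.2 and 10.** Tabulate compliance, and withdrawals for non-compliance, by the regimen in use at the time. Restore the summary of weekly-dosing duration and reasons for termination planned in protocol 17.7, or list its removal in SAP 18.

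**Protocol 5.4 and 9.7.** Reconcile them on how compliance is computed for weekly dosing and on whether the consequence is withdrawal from treatment or from the study. The clinical rule itself is for the sponsor.

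**Cost.** One revised definition, one restored summary and one extra split in two tables, with at most 50 weekly patients and so small counts. Because the SAP already describes enrolment as past, a protocol clarification may come too late to change conduct; the SAP changes need no new enrolment.

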## 6 Investigational Medicinal Products

### 6.1 Treatment Regimen

A schematic representation of the Treatment Regimen is presented in [Panel 3](#) below. The total treatment period is 52 weeks.

**For patients who completed study 16159A (*16159A-patients*)**

The Baseline Visit will take place at the same visit as the Visit 12 (Primary Outcome Visit, end of Week 16) of the study 16159A.

After the baseline assessment, for eligible patients, the treatment with Lu AF35700 will be initiated at daily dose of 10 mg at Day 1 of study 16159B. In addition, for *16159A-patients*, the treatment (Lu AF35700, risperidone or olanzapine) received during study 16159A will be tapered down in a blinded fashion with wallets from study 16159A and will be completed in 7 days according to the following scheme:

- Patients randomised to Risperidone: 4 mg/day for the first 3 days; 2 mg/day for the 4 subsequent days, encapsulated tablets, orally, once daily
- Patients randomised to Olanzapine: 10 mg/day for the first 3 days; 5 mg/day for the 4 subsequent days, encapsulated tablets, orally, once daily
- Patients randomised to Lu AF35700: Placebo for 7 days, encapsulated tablets, orally, once daily.

At the end of the first week (Week 1 Visit), all patients will be treated with 10 mg/day Lu AF35700 only.

From the Week 1 Visit, according to the investigator's clinical judgment, the 10 mg/day dose can be increased to 20 mg/day based on the patient's response. Thereafter, the 20 mg/day dose can be reduced to 10 mg/day based on the patient's tolerability to treatment. This can occur at scheduled or unscheduled visits.

From the Week 8 Visit, the switch from Lu AF35700 daily dosing regimen to Lu AF35700 weekly dosing regimen can be performed at any consecutive visit according to the investigator's clinical judgment. The first weekly tablet will be taken 7 days after the last daily tablet. The Lu AF35700 weekly dosing regimen can be switched back to a daily dosing regimen of 10 mg/day for tolerability reasons or to 20 mg/day for worsening of the patient's clinical status. This can occur at scheduled or unscheduled visits. The first daily tablet will be taken 7 days after the last weekly tablet.

The number of patients under weekly dosing regimen will be limited to 50 patients by IVRS/IWRS.

